Appendix 1-A (cont.) **Schedule of Assessments**

- ^q See [Appendix 2-A](#) for detailed explanation of PD biomarker assessments (Sets 1 and 2). Blood samples will be banked for 5 years for future exploratory PD biomarker analyses. Blood samples may also be drawn to conduct biomarker assays at the central laboratory on an unscheduled basis (at the clinical judgment of the investigator) at any time.
- ^r Following bypassing agent treatment, patients should provide a sample for local laboratory monitoring of thromboembolic events and thrombotic microangiopathy for platelet count, serum creatinine, LDH, and peripheral blood smear analysis for schistocytes within 24–48 hours of initial bypassing agent use. A plasma sample should also be provided for local laboratory monitoring of fibrinogen and D-dimer. For patients who require multiple doses of bypassing agents, laboratory monitoring should be performed every 24–48 hours thereafter until 24–48 hours following the last dose of bypassing agents administered to treat a given bleed. If applicable, laboratory results should be recorded in the Unscheduled Visit eCRFs
- ^s At the Week 1 visit, patients or their caregivers will be trained on how to use, and be provided with, their own electronic, handheld device. At subsequent visits, as marked, investigator review of patient-reported bleed/injection questionnaire information will be conducted. Information regarding trauma events in the preceding month will be collected in the eCRF by the investigator.

Appendix 1-B
Schedule of Assessments - Extension Phase

Extension Phase Schedule of Assessments — Arm A, B, C, and D				
	Extension Phase Day 1 ^a	Every 24 Weeks ^a	Extension Phase Completion/Extension Phase Early Termination ^b	Extension Phase Early Disc. Safety F/U Visit
Informed consent ^c	x			
Physical examination (including weight and height) ^d	x	x	x	x
Vital signs ^e	x	x	x	x
Concomitant medications ^f	x	x	x	x
Safety laboratory Assessments ^g	x	x	x	x
Adverse events ^h	x	x	x	x
IMP management ⁱ	x	x		
Emicizumab dispensing and administration ^j	x	x		
Following treatment with bypassing agents ^k	Monitoring for thromboembolic events and thrombotic microangiopathy			

Appendix 1-B (cont.) Schedule of Assessments - Extension Phase

Disc=discontinuation; ET=early termination; eCRF=electronic case reporting form; F/U=follow-up.

- ^a Assessments performed within \pm 14 day of visit.
- ^b In the event a patient discontinues emicizumab early before the study completion (*with the exception where the reason for discontinuation is the patient switching to commercial emicizumab product*), an early discontinuation safety follow-up visit should be performed 24 weeks after discontinuation of emicizumab.
- ^c Obtain a separate written informed consent (or patient's assent and caregiver written informed consent if patient is an adolescent/pediatric) before transferred to extension phase.
- ^d Calculation of dose based on weight is required. A complete physical examination will be performed at extension phase Day 1 and at least a targeted physical examination will be performed at subsequent visits. Targeted physical examination of joints (for bleeds, evidence of arthropathy) and skin (for bruises, hematomas, and injection-site reactions) as clinically indicated and/or with report of new or worsening adverse event. Height will be measured at extension phase Day 1 and annually.
- ^e Body temperature (oral or tympanic), blood pressure, pulse rate, and respiratory rate only to be used to monitor hypersensitivity reactions during and after injection and not to be entered on eCRF, except at study completion/early termination. Weight will be measured and recorded in the eCRF at each visit prior to any injections (if applicable).
- ^f Concomitant medications (e.g., extra pain medication with bleed) will be asked about at the time of the scheduled visit, excluding treatments for bleeds (i.e., FVIII and other medications to treat bleeds), which will *not* be collected during the study extension phase.
- ^g Safety laboratory assessments should be performed *at least once every 12 months*, including complete blood count with differential (i.e., neutrophils, hemoglobin, platelet count) and serum chemistries (i.e., potassium, creatinine, total and direct bilirubin, albumin, alanine aminotransferase, aspartate aminotransferase, and alkaline phosphatase), PT, APTT, and INR. Investigators may choose to add any additional tests to be processed in the local lab at clinical discretion.
- ^h Injection-site reaction adverse events will be collected on a separate form from the adverse event form. If there is unexpected worsening of the patient's hemophilia in terms of severity (e.g., increased number of doses of FVIII to stop bleeds compared with before study entry), frequency of bleeds, or nature at any time during the study, this should be documented as an adverse event on the Adverse Event eCRF, conveying that the underlying condition has changed by including applicable descriptors (e.g., "increased clinical severity of hemophilia").
- ⁱ Drug dispensation will not occur at the study completion/early termination visit.
- ^j For patients randomized to Arm A: emicizumab 1.5 mg/kg QW subcutaneously. For patients randomized to Arm B: emicizumab 6 mg/kg Q4W subcutaneously. For patients randomized to Arm C: 6 mg/kg Q4W subcutaneously. For patients in Arm D: 1.5 mg/kg QW subcutaneously. Patients should record their actual Emicizumab administer in their handheld device.
- ^k Following bypassing agent treatment, patients are recommended to provide a sample for local laboratory monitoring of thromboembolic events and thrombotic microangiopathy for platelet count, serum creatinine, LDH, and peripheral blood smear analysis of schistocytes within 24–48 hours of initial bypassing agent use. A plasma sample can also be provided for local laboratory monitoring of fibrinogen and D-dimer. For patients who require multiple doses of bypassing agents, laboratory monitoring is recommended every 24–48 hours thereafter until 24–48 hours following the last dose of bypassing agents administered to treat a given bleed. If applicable, laboratory results should be recorded in the Un scheduled Visit eCRFs.

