Protocol YO39309 has been primarily amended to extend the study. The study will end 3 years after the last Arm D patient completes 1 year treatment and patients still having clinical benefit are transferred to a post-trial continued access solution per Roche Global Policy on Continued Access to Investigational Medicinal Products (see Sections 3.1 and 4.3.4). The study will end earlier, before 3 years after the last Arm D patient completes 1 year treatment, should the post-trial continued access solution be available earlier (see Section 3.2.1). Changes to the protocol, along with a rationale for each change, are summarized below:

- Language has been added to clarify that collection of pharmacokinetic (PK)/anti-drug antibody (ADA)/Biomarker samples from Arm D patients will stop when the patient completes the study or after Week 49, whichever occurs first (Section 3.1).
- Language has been added to clarify that patients who discontinue treatment prior to the end of study will return to the clinic for a safety follow-up visit 24 weeks after the final dose of study drug (Section 3.2.1).
- The length of study has been extended to 88 months to include a study Extension Phase because the study had been extended for 3 years after last Arm D patient completes 1 year of treatment and patients still having clinical benefit are transferred to a post-trial continued access solution. This is to allow patients who are still benefiting from emicizumab to continue treatment and to collect their safety data during the extended treatment (Section 3.2.2 and Appendix 1-B).
- Language has been added to indicate that sites can confirm that appropriate temperature conditions have been maintained during Investigational Medicinal Product (IMP) transit either by time monitoring (shipment arrival date and time) or temperature monitoring (Section 4.3.3).
- Language has been added to clarify that the Bleed/Medication questionnaire devices will remain with the patient/caregiver for the duration of the study. Bleed and medication data will not be collected during the study extension phase, but emicizumab dosing data will continue to be collected (Section 4.5.7).
- Language has been added to clarify that adverse events associated with a special situation that also qualify as adverse events of special interest should be reported within 24 hours (Section 5.3.5.12).

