4.5.7 Patient-Reported Outcomes

To capture bleed and hemophilia medication use data, as well as HRQoL and health status data during study treatment, patients/caregivers will complete the Bleed/Medication questionnaires on an electronic, handheld device that will be provided to them during their Week 1 visit at the site. This device will remain with the patients/caregiver for the duration of the study to enter bleed and medication data on a weekly basis at minimum *before the study extension phase. After the start of the extension phase, bleed and medication data will not be collected.* Patients and/or caregivers will complete HRQoL, proxy HRQoL-SF, and aspects of caregiver burden questionnaires at designated timepoints during clinic visits on a separate electronic, handheld device (tablet) that will remain at sites. The electronic, handheld device and instructions for completing the questionnaires will be provided by the investigator staff. The questionnaires should be completed by the patient or their caregivers at the site at the start of the visit and prior to all other study assessments.

After bleed, medication, HRQoL, proxy HRQoL, and aspects of caregiver burden entries have been saved, the data will be transmitted automatically from the respective devices to a centralized vendor database. Bleed and medication use data entered since the

patient's previous clinic visit will be reviewed at subsequent clinic visits, as per the schedule of assessments, for completeness and accuracy. Investigators will review the bleed and bleed medication data as per the schedule of assessments (see [Appendix 1](#)) and have the ability to correct or complete entries once verified with the patient/caregiver using a Data Change Request Form process or via a Web-based portal, once implemented.

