5.1.2 Risks Associated with Emicizumab

5.1.2.1 Identified Risks

Thrombotic Microangiopathy (Associated with Emicizumab and aPCC)

Thrombotic microangiopathy is a very rare, but serious condition whereby microvascular thrombosis leads to organ damage.

As of October 2018, among 417 patients in five studies (ACE002JP, BH29884, BH29992, BH30071, and BO39182), there were 3 patients (1.0%), all in Study BH29884, who experienced thrombotic microangiopathy while receiving emicizumab prophylaxis. These events are believed to be caused by an interaction between emicizumab and aPCC, as all 3 patients received cumulative doses of >100 U/kg/day on average of aPCC for ≥24 hours for the treatment of breakthrough bleeds just prior to developing symptoms. These events were reported as serious adverse events (two Grade 4 events and one Grade 3 event). One patient died due to a serious adverse event of Grade 4 rectal haemorrhage (assessed as unrelated to emicizumab). From additional analyses, including data on the thrombotic microangiopathy and thromboembolic events,

there is evidence to support a drug-drug interaction between aPCC and emicizumab. Please see the Emicizumab Investigator's Brochure for a complete summary of safety information.

Specific guidance regarding the use of bypassing agents in combination with emicizumab is detailed in Section 4.4.1.

Any thrombotic microangiopathy event should be reported as an adverse event of special interest and also as a serious adverse event, if it meets criteria for such (see Section 5.2.2 and Section 5.2.3).

Guidelines for management of patients who develop thrombotic microangiopathy are provided in Section 5.1.3.

Hypercoagulation and Risk of Thrombosis

As of October 2018, four thromboembolic events have been reported in 3 patients with hemophilia A with inhibitors while receiving emicizumab in Study BH29884.

Two patients who administered cumulative doses of > 100 U/kg/day on average of aPCC for ≥24 hours while receiving emicizumab developed thromboembolic events. The thromboembolic events were reported as serious adverse events (Grade 3 cavernous sinus thrombosis, Grade 3 skin necrosis, and Grade 2 thrombophlebitis superficial); however, none were life-threatening or fatal. No anticoagulation was started and symptoms in both patients improved with supportive care. These adverse events are believed to be caused by a drug-drug interaction between emicizumab and aPCC.

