Appendix 1-A (cont.) Schedule of Assessments

- ⁱ Laboratory data (performed locally) include: complete blood count with differential (i.e., neutrophils, hemoglobin, platelet count), serum chemistries (i.e., sodium, potassium, glucose, blood urea nitrogen, creatinine, calcium, phosphorus, magnesium, total and direct bilirubin, albumin, alanine aminotransferase, aspartate aminotransferase, and alkaline phosphatase). Laboratory assessments completed at the screening visit do not have to be repeated at Week 1, if the period between screening and Week 1 is 5 days or less and there has been no change in health status as assessed by the investigator. Patients with childbearing potential will be required to have a negative serum pregnancy test result at screening (and within 7 days of study drug initiation, if applicable) and urine pregnancy tests performed at every clinic visit, with the exception of Weeks 2–4 and 7. Patients on Arm C will have urine pregnancy test performed at screening and before starting emicizumab (Week 25).
- ^j Concomitant medications (e.g., extra pain medication with bleed) will be asked about at the time of the monthly assessment, excluding treatments for bleeds (i.e., FVIII and other medications to treat bleeds), which will be collected on the bleeding questionnaire.
- ^k Performed locally. If screening ECG is abnormal, repeat at Week 1 (or Week 2 if screening and Week 1 occur on the same day), otherwise do not repeat. ECGs will also be performed 4–8 and 24 weeks after starting emicizumab or dose up-titration, as well as at study completion/early termination.
- ^l Reported by the patient or their caregivers and includes: start date and time, reason, type, location, and associated symptoms for joint and muscle bleeds, as well as start date and time, reason, type, and dose of each injection, excluding emicizumab.
- ^m Injection-site reaction adverse events will be collected on a separate form from the adverse event form. If there is unexpected worsening of the patient's hemophilia in terms of severity (e.g., increased number of doses of FVIII to stop bleeds compared with before study entry), frequency of bleeds, or nature at any time during the study, this should be documented as an adverse event on the Adverse Event eCRF, conveying that the underlying condition has changed by including applicable descriptors (e.g., "increased clinical severity of hemophilia").

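### The extension phase ends routine recording of bypassing agents given for bleeds, so an absence of thrombotic events cannot be told apart from an absence of exposure

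*Protocol*

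**What the plan says.** The protocol's amendment rationale gives two reasons for extending the study: "to allow patients who are still benefiting from emicizumab to continue treatment and to collect their safety data during the extended treatment". Appendix 1-B then sets visits every 24 weeks covering adverse events, safety laboratory tests, concomitant medications and emicizumab supply and dosing. On bleed treatments it and the related sections say:

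- Section 4.5.7, repeated in Section 4.5.8.2: "After the start of the extension phase, bleed and medication data will not be collected".
- Appendix 1-B, footnote f: concomitant medications are asked about at each visit, "excluding treatments for bleeds (i.e., FVIII and other medications to treat bleeds), which will" not "be collected during the study extension phase".
- Appendix 1-B, footnote j, on what the device still captures: "Patients should record their actual Emicizumab administer in their handheld device".
- Appendix 1-B, footnote k: "Following bypassing agent treatment, patients are recommended to provide a sample for local laboratory monitoring of thromboembolic events and thrombotic microangiopathy". Laboratory results, where applicable, go on the Unscheduled Visit eCRF.
- Section 5.1.2.1, on the three thrombotic microangiopathy cases: "These events are believed to be caused by an interaction between emicizumab and aPCC". It gives the same explanation for the thromboembolic events in two patients.

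Section 4.4, by contrast, has every concomitant medication up to the completion or discontinuation visit entered on the Concomitant Medications eCRF, and makes no exception for the extension.

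**The concern.** In the main phase, leaving bleed treatments off the concomitant-medication record loses nothing. Appendix 1-A, footnote j, explains that these are the treatments "which will be collected on the bleeding questionnaire". The extension keeps the exclusion and removes the questionnaire that made it harmless.

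The protocol links its most serious identified risks to a drug given for breakthrough bleeds. Thrombotic microangiopathy and thromboembolic events remain adverse events of special interest (Section 5.2.3), so cases will be reported. What is lost is the set of patients who took the interacting product and had no event. A summary showing no such events could then mean that the combination was tolerated or that nobody received it. Nor could anyone check whether the monitoring in footnote k was done each time it applied.

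**Working it through.** The plan gives no figure for this point, so the check is mainly textual, with some arithmetic for size.

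**Step 1. Routes by which a bypassing agent given for a bleed could be recorded in the extension.**
- Bleed/medication questionnaire: stopped (Sections 4.5.7 and 4.5.8.2).
- Concomitant-medication record: excluded (footnote f).
- Handheld device: footnote j asks only for emicizumab doses.
- Bleeds themselves: Section 5.2.1 keeps new non-serious bleeds off the eCRF because the questionnaire holds them, and the questionnaire no longer runs.
- Footnote k: calls for laboratory results, not the product, dose or date that prompted the test.

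No routine route remains.

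**Step 2. Internal conflicts.**
- Section 4.4 requires all medications to be recorded; footnote f excludes one class.
- Footnote k makes monitoring depend on an exposure that is not captured.
- Footnote h asks for more treatment doses per bleed, or more frequent bleeds, to be reported as a worsening of hemophilia, although neither is now collected.

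**Step 3. Which exposure matters.** Section 5.1.2.1 names aPCC at cumulative doses averaging above 100 U/kg/day for at least 24 hours. Section 4.4.1 treats aPCC and PCC alike in its caution. Section 1.1.1 lists PCC and rFVIIa as the products available in China. Section 3.1 takes at least 60 randomized patients from China and all of Arm D from the mainland. Emicizumab with PCC is therefore a plausible exposure in this study.

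**Step 4. Size.** Inputs: 70 randomized patients, at most 55 of them without inhibitors, and 15 Arm D patients, all with inhibitors (Section 3.1); 3 years from the last Arm D patient's first treatment year (Section 3.2.2). Appendix 9 does not expect bypassing agents in patients without inhibitors.
- Randomized inhibitor patients with the cap filled: 70 − 55 = 15.
- All inhibitor patients: 15 + 15 = 30.
- Person-time in the 3-year window if all continue: 30 × 3 = 90 patient-years.

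**Step 5. Expected events, for context.** The pooled experience is 3/417 = 0.72% for thrombotic microangiopathy (exact 95% CI 0.15% to 2.09%) and 2/417 = 0.48% for patients with thromboembolic events attributed to aPCC (0.06% to 1.72%). Applying 3/417 gives 30 × 3/417 ≈ 0.2 expected thrombotic microangiopathy cases among 30 patients and 85 × 3/417 ≈ 0.6 among all 85. This assumes that the pooled per-patient risk carries over, which the documents do not establish.

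**The case against.** The strongest reply is that dropping the diary is a deliberate simplification of a phase whose first purpose is continued treatment, and that the exposures of most concern would surface anyway. Section 4.3.2 sends events needing multiple daily administrations to the Medical Monitor immediately. Section 4.4.1 allows repeated bypassing-agent dosing only under medical supervision with laboratory monitoring. Section 4.4.2 has prohibited therapy, which includes aPCC/PCC for short-term prophylaxis, recorded on the eCRF. Any event of special interest will carry case details. Safety analyses are descriptive (Protocol Section 6.5, SAP Section 4.7), no rate per exposure is planned, and with well under one expected case such a rate would say little.

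Most of this stands, and it limits the point. It does not supply the missing record: these routes pick up particular uses, not all exposed patients. With few events expected, the likeliest result is none, and that is the result that cannot be read without knowing who was exposed.

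Four stronger readings might be inferred; the documents do not support them.
- *Bypassing agents as a class are the named cause.* Section 5.1.2.1 names aPCC. It reports no thromboembolic events with emicizumab plus rFVIIa alone, and one device occlusion without any bypassing agent.
- *All follow-up of all patients is affected.* 85 × 3 = 255 patient-years counts patients without inhibitors, in whom these agents are not expected. A share of three quarters assumes one main-phase year for everyone, but Appendix 1-A continues 12-weekly visits from Week 61 and the protocol gives no individual entry dates. By calendar, 36 of 88 months is 41%.
- *The safety aim is defeated.* Adverse events, laboratory tests and emicizumab dosing are still collected.
- *Only patients with an event or an unscheduled test leave any trace.* The routes above show otherwise.

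**Conclusion.** The point holds as a gap in exposure data and an unreconciled conflict between sections. Routine recording of bleed treatments ends in the extension, contrary to Section 4.4. Exposed patients without an event therefore cannot be systematically identified, and completion of footnote k monitoring cannot be verified.

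It affects mainly inhibitor patients: about 30, contributing at most about 90 patient-years in the 3-year window. This rests on full enrolment, a filled 55-patient cap and no patient leaving. It would be larger if fewer patients without inhibitors enrolled, and smaller with dropout or the early study end that Section 3.2.1 allows. Any extension time before the window opens would add to it.

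The gain from closing the gap lies in interpreting descriptive safety data. It would not yield a usable event rate, and the primary efficacy analysis is not affected.

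**What to change.** Reconcile Section 4.4, Sections 4.5.7 and 4.5.8.2, Appendix 1-B footnotes f and k, and the matching item in the amendment rationale. They should all say that any aPCC/PCC, rFVIIa or other bypassing agent taken in the extension is recorded, with product, dates and dose, on the existing Concomitant Medications eCRF at the scheduled 24-weekly visits. Editing footnote f alone would leave Sections 4.5.7 and 4.5.8.2 saying that medication data are not collected. FVIII and the bleed diary may stay excluded. This is data capture only: no dose, treatment or monitoring rule changes.

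The cost is a few eCRF entries per visit, mainly for inhibitor patients, at visits where concomitant medications are already asked about. The downside is recall over up to 24 weeks, so dates and doses will be approximate. Even an imperfect record shows who was exposed, which makes this a cheap improvement.
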